2.2 Secondary Objectives (if applicable)

- Salivary melatonin levels on PICU day two and five
- Nighttime EEG slow-wave activity during endotracheal intubation with EMG and EOG
- R2 feasibility, adherence, system barriers
- Levels of patient comfort: PICU days free of pain, agitation, delirium, iatrogenic withdrawal
- PICU exposure to sedative medications (total dose and length of exposure)
- Time to physiological stability (time on vasoactive medication, duration of mechanical ventilation, PICU and hospital length of stay)
- Parent perception of being well-cared-for

3 Investigational Plan

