3.3 Study Measures

All patients will be enrolled within 24 hours of PICU admission. Using medical records, patient monitoring and environmental monitoring, the following data will be collected for this study.

Baseline and Intervention Phase:

- 1) Patient comfort will be measured using the following scale, as applicable:
 - a. Pain assessed using either the Face, Legs, Activity, Cry, Consolability (FLACC) scale in nonverbal children 0 to 6 years of age, the individualized numeric rating scale (INRS) in nonverbal cognitively impaired children age 6 and older, or the Wong-Baker Faces Pain Scale (WBFPS) in verbal children age 3 and older. All pain scales range 0-10 with higher scores indicating more pain.
 - b. Level of sedation in intubated patients is assessed using the State Behavioral Scale (SBS). 71 SBS scores range from -3 (unresponsive) to +2 (agitated).
 - c. In patients receiving neuromuscular blockade, pain/agitation is judged to be present by the bedside nurse when a patient demonstrates a $\geq 20\%$ increase in heart rate or blood pressure when stimulated.
 - d. Delirium is assessed using either the Cornell Assessment for Pediatric Delirium (CAPD), or the preschool/pediatric CAM instruments; all are rapid bedside screeners for delirium in hospitalized children.
 - e. Patients weaning from ≥ 5 days of sedation are monitored for IWS using the Withdrawal Assessment Tool-1 (WAT-1). The WAT-1 scale ranges 0-12 with higher scores indicating more withdrawal symptoms.
 - f. Percentage of total ICU days with no pain, agitation, delirium, or IWS will be monitored and reported.
- 2) Child's Daily Routine and Sleep Survey – completed at enrollment by a parent
- 3) Exposure to sedative medications – per medical record
- 4) The duration of time between the start and stop of all vasoactive medications, from endotracheal intubation to successful endotracheal extubation, from PICU admission to PICU discharge, and from hospital admission to hospital discharge – per medical record
- 5) Light and noise monitoring - recorded continuously using Quietyme technology
- 6) EEG, EOG and EMG monitoring for up to 72 hours- EEG will consist of 2 central leads in addition to EOG and EMG (1 lead each on outer corner of the eye and one on the chin).
- 7) Actigraphy monitoring (placed on wrist or ankle at enrollment) – recorded continuously
- 8) Saliva Samples – collected with an oral swab eight times across two days (Day 2 & Day 5)

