5.1 Screening

Screening activities will take place daily at 10am +/- 2 H for this study. The research coordinator will review the medical records of all PICU admissions within the past 24 hours for demographic and clinical condition to determine initial eligibility. The research coordinator will confirm each potential patient's eligibility with the patient's care team and attending physician. Upon confirmation of eligibility the clinical team will introduce the patient's parent/legal guardian to the study and the research coordinator. For parents/legal guardians interested in participation, informed consent will be obtained.

The following table provides a review of the data collection timeline for this study:

Measurement	Screening	Day 1	Day 2 & Day 5	Daily	PICU Discharge
Demographic Data	X	X			
PCPC/POPC score	X	X			
Medical History	X	X			
PRISM III		X			
Child's Daily Routine and Sleep Survey		X			
Salivary Swab			X		
Ventilation Status, sedative medications, neuromuscular blockades, extubation readiness test				X	
Pain, Sedation, Delirium Scores				X	
WAT-1 Iatrogenic Withdrawal Syndrome assessment				Weaning phase	
Enteral nutrition pattern/volume				X	
Occupational/Physical/Child life therapy				X	
Sound/Light monitoring				X	
EEG monitoring				X (3 days)	
Ankle/wrist Actigraphy				X	
Activity Log				X	
Parent Diary				X	
Family Centered Care Scale (FCCS)					X

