The investigator will permit study-related monitoring, audits, and inspections by the EC/IRB, the sponsor, government regulatory bodies, and University compliance and quality assurance groups of all study related documents (e.g. source documents, regulatory documents, data collection instruments, study data etc.). The investigator will ensure the capability for inspections of applicable study-related facilities (e.g. pharmacy, diagnostic laboratory, etc.).

10 *Ethical Considerations*

10.1 *Risks*

Privacy and Confidentiality: Strict measures will be taken to ensure participant privacy and confidentiality. All data will be de-identified then stored in the secure REDCap database or in the Excel database, as appropriate. Specimens will be de-identified and stored in lockable research freezers, and each participant will be assigned a unique identification number. The master list linking identification numbers to identifying information will be stored separately from the study database. All personally identifiable information will be kept strictly confidential and stored in an encrypted document, on a dedicated research server only accessible by the research team.

Risk associated with EEG and ankle/wrist monitoring includes irritation at the site and will be minimized by scheduled assessments of the sites, and removal of the device if irritation or redness occurs.

The major components of RESTORE are a standard of care in each PICU. The current study is testing the feasibility of implementing the entire 7-item bundle of activities/clinical care within a PICU, it is not testing each item within the bundle. Risk associated with over and /or under sedation will be minimized by hourly assessment of goal SBS attainment with the subject is intubated.

Risks associated with bolus feed included gastro-esophageal reflux and aspiration. However, children who are at risk for reflux and aspiration will be excluded from the study. Children who have clinical signs of aspiration will be removed from study. Reflux precautions including head of bed at 300 will be implemented when appropriate.

Risks from progressive mobility include inadvertent tube/catheter dislodgement. However, these risks are minimized since the care models at both Johns Hopkins and CHOP have incorporated progressive mobility as part of the standard of care, and are well trained with this intervention. Children at high risk for tube and or catheter dislodgment will not participate in this activity.

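### Over-sedation is a named risk, yet no planned outcome or by-phase summary uses the low end of the SBS, and the comfort-day measure as written credits unresponsive days

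*Combined protocol and SAP*

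**What the plan says.** Section 10.1 (Risks) treats sedation depth as a two-sided hazard: "Risk associated with over and /or under sedation will be minimized by hourly assessment of goal SBS attainment with the subject is intubated".

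Section 3.3 (Study Measures), under the measures for both phases, gives the instrument in item 1b: "Level of sedation in intubated patients is assessed using the State Behavioral Scale (SBS"), and "SBS scores range from -3 (unresponsive) to +2 (agitated"). The data collection table in section 5.1 has a row "Pain, Sedation, Delirium Scores", marked for daily collection.

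The outcome built from these assessments is the comfort measure. Section 2.2 lists it as a secondary objective: "Levels of patient comfort: PICU days free of pain, agitation, delirium, iatrogenic withdrawal". Section 3.3, item 1f, states how it is expressed: "Percentage of total ICU days with no pain, agitation, delirium, or IWS will be monitored and reported". The Study Summary plans t-tests or Wilcoxon rank-sum tests for continuous secondary outcomes, so this percentage will be compared between the Baseline and Intervention Phases.

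Section 2.2 also lists sedative exposure, as total dose and duration.

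**The concern.** The SBS has two ends, and section 10.1 counts both as risks. The comfort measure has a component for one of them, agitation. A child who is unresponsive all day and has no pain, agitation, delirium or withdrawal recorded meets item 1f as written, so the day adds to the comfort percentage.

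This matters more here than in most studies. Keeping sedation to the least that works is element 3 of the bundle (section 2), and the rationale in section 1 is that critically ill children can safely be kept more awake. If the bundle lightens sedation, some days that would have been credited as unresponsive become days on which pain or agitation can be seen and scored. The comfort comparison could then favour the phase with deeper sedation, and nothing else in the planned output would show why. The results are meant to inform a larger randomized trial, so a misread comfort difference could carry over into that design.

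**Working it through.** No figure in the plan can be reproduced here. The check is a reading of every place where sedation depth could be reported, followed by arithmetic on assumed values.

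**Step 1. Where SBS or sedation appears**

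| Place | What it provides | Depth of sedation by phase? |
|---|---|---|
| 2.2 and 3.3 item 1f | Days free of four problems | No; agitated end only |
| 2.2 and 3.3 item 3 | Sedative dose and duration | No; drug given, not depth reached |
| 3.3 item 1b and 5.1 table | SBS scored, sedation scores collected daily | Data exist, no summary planned |
| 3.3, Intervention Phase items 1 and 4 | Adherence form; sedation per RESTORE | No; one phase only, SBS content not stated |
| Study Summary statistics and section 6 | General methods | No SBS summary named |
| Section 7 | Any undesirable experience recorded, monthly summary | Over-sedation not named, no SBS criterion |
| 10.1 | Hourly bedside check against goal SBS | A care safeguard, not a reported summary |

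**Step 2. How item 1f treats a child who shows no behaviour**

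Item 1c gives a physiological rule for judging pain or agitation under neuromuscular blockade: a rise of at least 20% in heart rate or blood pressure on stimulation. So the plan deals with one group that cannot show behaviour. It has no matching provision for a child unresponsive from sedation, and item 1f has no rule for such a day.

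**Step 3. Size, on assumed values**

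Let d be the share of a phase's ICU days at SBS -3, f the share of those days counted as free, and c the share of all other days counted as free.

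- Comfort share: C = d × f + (1 − d) × c.
- With the same f and c in both phases, C_base − C_int = (d_base − d_int) × (f − c).

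The documents give none of d, f or c. Take c = 60% and f = 100% (every day at -3 is credited).

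- Baseline with d = 20%: 0.20 + 0.80 × 0.60 = 68%.
- Intervention with d = 10%: 0.10 + 0.90 × 0.60 = 64%.
- Baseline looks 4 points more comfortable although c is identical in the two phases.

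For other gaps in d: 0.05 × 0.40 = 2 points, 0.10 × 0.40 = 4 points, 0.20 × 0.40 = 8 points.

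Sensitivity to the assumptions, from the same formula: with f = 100%, the shift is nil if c = 100% and equals the whole gap in d if c = 0. If f = c, there is no shift at all.

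**Step 4. What a version without the credit would show**

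Setting f = 0 and keeping the days in the denominator gives Baseline 0.80 × 0.60 = 48% and Intervention 0.90 × 0.60 = 54%, a 6-point difference the other way. The two versions (+4 and −6 points for Baseline minus Intervention) bracket the comparison. Neither is the true value; the share of days at -3 is what explains the distance between them.

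**The case against.** Several points on the other side stand.

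- A reader might infer that the SBS scores serve no purpose beyond the comfort measure. They do: section 10.1 uses them for hourly goal checks at the bedside.
- A reader might infer that over-sedation would never be reported. The documents do not support that. Section 7 records any undesirable experience and summarizes adverse events monthly, and sedative exposure and duration of ventilation are secondary outcomes. None of these reports depth of sedation by phase.
- A reader might infer that every day at SBS -3 counts as comfortable. Item 1f gives no cut-off for any component and no rule for days that cannot be assessed. One score of -3 does not make a whole day unresponsive, and the day can still fail on pain, delirium or agitation at another hour. The documents do not say how the pain and delirium tools score an unresponsive child.
- A reader might infer that the comparison is biased against the bundle. RESTORE is described as standard care at both sites (Study Summary; section 10.1), so depth may differ little by phase. Section 4.3 says bundle elements are used only sporadically at the sites, so a difference is possible, but its direction is not known.
- Single-patient examples can be built to reverse the sign. Suppose a child has 8 days, 2 at SBS -3 and 2 others with pain or agitation, and so scores 6/8 = 75%. If both days at -3 become responsive and one includes agitation, the score falls to 5/8 = 62.5%. If neither does, it stays at 6/8. The result is set by the assumption.
- This is one secondary outcome in an exploratory pilot of 60 subjects with no power claim (sections 6.1 and 6.2), and the study tests the bundle as a whole (section 10.1).

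These points limit the claim and argue against replacing the stated outcome with a new rule. They do not supply the missing summary.

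**Conclusion.** The point holds as a reporting gap. Over-sedation is a named risk and the scores that measure it are collected in both phases, but no planned outcome or by-phase summary uses the low end of the scale. As written, item 1f credits a day at SBS -3 on which none of its four problems is recorded. If depth of sedation differs between phases, the comfort comparison can therefore favour the more sedated phase.

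The size and direction of any effect cannot be derived from the documents. The 2, 4 and 8 points for gaps of 5, 10 and 20 points in days at -3 rest on two assumptions, a 60% free share on other days and full credit for days at -3, and on both shares being equal in the two phases. Nothing here shows that a distortion will occur, only that the planned output could not reveal one.

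**What to change.** Keep item 1f as the stated secondary outcome and add two items to sections 3.3 and 6, both drawn from sedation scores already recorded.

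1. Next to the comfort percentage, report by phase the share of SBS assessments (or days) at -3 and the share at the agitated end, restricted to intubated time without neuromuscular blockade.
2. Add a sensitivity analysis of comfort days that does not credit days at SBS -3 but keeps them in the denominator. State before analysis which of a day's recorded scores decides that it is a day at -3, and read the result as the opposite bound to item 1f.

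Report attainment of goal SBS only if the goal is already in the study data. The section 5.1 table lists sedation scores but no goal, and the hourly check in section 10.1 is described as bedside care.

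The cost is a few sentences and a little more analysis. In the sensitivity version the comfort percentage falls by the share of ICU days that lose their credit. The change concerns reporting only and sets no sedation target or clinical rule.

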3.4 Study Endpoints

3.4.1 Primary Study Endpoint

The study endpoint will be PICU discharge or PICU day 28, whichever occurs first.

4 Study Population and Duration of Participation

The target population for this study is pediatric patients admitted to the PICU between the ages of 6 months and 18 years who are intubated and mechanically ventilated for acute airways or parenchymal disease, and are expected to be intubated for more than 24 hours.

4.1 Duration of Study Participation

Subject participation will last until PICU discharge or Day 28, whichever occurs first.

4.2 Total Number of Subjects and Sites

No subjects will be enrolled at Penn. Two sites, Children's hospital of Philadelphia and Johns Hopkins Children's Center, will each enroll 30 subjects who provide full usable data (10 baseline/control and 20 intervention).

4.3 Inclusion Criteria

The following is a list of study inclusion criteria:

- PICU admission at one of the study sites in which elements of R2 are typically but sporadically implemented
- Transferred to the PICU from another hospital unit/ward with ≤ 4 nights in the hospital (≤ 2 nights in PICU)
- Between the ages 6 months and 18 years at the time of enrollment (has not had their 18th birthday)
- Intubated and mechanically ventilated for acute airway or parenchymal disease within last 48 hours
- Expected to be intubated for more than 12 hours past enrollment
- Parent/Guardian providing consent, provides primary care for subject

4.4 Exclusion Criteria

The following is a list of exclusionary criteria for this study:

- A baseline cognitive dysfunction, measured by the Pediatric Cerebral Performance Category (PCPC ≥ 4)
- A history of an uncontrolled seizure disorder (seizure within past 3 months), cerebral hypertension, neuromuscular respiratory failure, ventilator dependence (excluding BiPAP or CPAP at night)
- A history of inability to tolerate bolus enteral feeds (full J-Tube fed patients)

CONFIDENTIAL

- The presence of any of the following within 24 hours of admission:
 - Modal pain scores greater than 4
 - Persistent hypotension/hypertension unresponsive to standard therapies
 - Use of High Frequency Oscillatory Ventilation or Extracorporeal Membrane Oxygenation
- Administered melatonin within the past week
- Has an active do-not-resuscitate plan

4.5 Subject Recruitment

Subjects for this study will be recruited via daily PICU admission logs. Consecutive patients admitted to the PICU at each of the study sites will be reviewed for eligibility (based on medical record) and if eligible invited to participate. After verifying the patient's eligibility status, the patient's legal guardian or parent(s) will be introduced to the research team by a member of the patients care team and informed consent will be requested from the parent or legal guardian. Recruitment will end when 60 subjects are enrolled.

4.6 Vulnerable Populations:

This study involves children. At the time of enrollment, the patient's legal guardian/parents will be introduced to the research team by a member of the patient's care team and informed consent will be requested from the parent or legal guardian. Due to existing medical conditions (e.g. sedation, mechanical ventilation) minor assent will not be obtained. Although not directly targeted, mentally disabled persons, economically or educationally disadvantaged persons, and/or employees or students of the University of Pennsylvania or other involved institutions will not be denied enrollment and any special protections and/or additional safeguards will be undertaken in order to protect the rights and welfare of these subjects from coercion or undue influence as appropriate.

5 Study Procedures

Following informed consent, during the baseline phase, all patient care will be managed at the discretion of the clinical care team. The study will not provide care recommendations or changes to treatment during the baseline phase.

The following procedures will occur daily during the Baseline and Intervention Phases:

- Completion of the Child's Daily Routine and Sleep Survey
- Patient Activity Log completed by parent or nurse
- Light and noise monitoring within the patient room using Quietyme technology
- Patient EEG monitoring (4 leads) for first 72 hours following enrollment
- Patient actigraphy monitoring (placed on wrist or ankle)

The following activity will occur twice during the study - on Day 2 and Day 5

- 1) Saliva Samples – an oral swab will be collected a total of eight times per day/2 days (16 total)
 - a. A small cotton swab (Salimetrics, Inc, PA) will be placed under the child's tongue for 60-90 seconds then inserted into a storage tube

In addition to those listed above, the following procedures will only occur during the Intervention Phase:

- Use the Child's Daily Routine and Sleep survey data to replicate the child's pre-hospitalization daily routine (bedtime/wake time, bedtime/arousal routine, nap time, feeding schedule, active periods) modulate the PICU environment and child activity
- Window shades and ambient lighting will be modified to provide day/night cycling per child's routine
- Light and sound will be modified throughout the day to match the child's preference and parent reporting

- Sedation managed per RESTORE principles within the PICU's standard of care.
- Enteral feeding will be provided during the day according to the child's routine
- Physical therapy and progressive mobility/exercise will be implemented per the PICU Up! program
- The PICU charge nurse will limit the number of nurses assigned to care for the subject
- Parents will be asked to complete daily diary entries via paper or electronic format

5.1 Screening

Screening activities will take place daily at 10am +/- 2 H for this study. The research coordinator will review the medical records of all PICU admissions within the past 24 hours for demographic and clinical condition to determine initial eligibility. The research coordinator will confirm each potential patient's eligibility with the patient's care team and attending physician. Upon confirmation of eligibility the clinical team will introduce the patient's parent/legal guardian to the study and the research coordinator. For parents/legal guardians interested in participation, informed consent will be obtained.

The following table provides a review of the data collection timeline for this study:

Measurement	Screening	Day 1	Day 2 & Day 5	Daily	PICU Discharge
Demographic Data	X	X			
PCPC/POPC score	X	X			
Medical History	X	X			
PRISM III		X			
Child's Daily Routine and Sleep Survey		X			
Salivary Swab			X		
Ventilation Status, sedative medications, neuromuscular blockades, extubation readiness test				X	
Pain, Sedation, Delirium Scores				X	
WAT-1 Iatrogenic Withdrawal Syndrome assessment				Weaning phase	
Enteral nutrition pattern/volume				X	
Occupational/Physical/Child life therapy				X	
Sound/Light monitoring				X	
EEG monitoring				X (3 days)	
Ankle/wrist Actigraphy				X	
Activity Log				X	
Parent Diary				X	
Family Centered Care Scale (FCCS)					X

5.1.1 End of Study Visit

None required

5.2 Subject Withdrawal

Subjects may withdraw from the study at any time without impact to their care. They may also be discontinued from the study at the discretion of the Investigator for lack of adherence to intervention or

CONFIDENTIAL

This material is the property of the University of Pennsylvania.

study procedures or visit schedules, AEs, or due to a change in medical history (e.g. develop an exclusionary medical condition or medication). The Investigator may also withdraw subjects who violate the study plan, to protect the subject for reasons related to safety or for administrative reasons. It will be documented whether or not each subject completes the study. Subjects who withdraw early will have one final visit to collect final evaluations and assess adverse events.

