5.2.1 Data Collection and Follow-up for Withdrawn Subjects

Subjects who withdraw consent to participate in the study will be seen for one final study visit. During this visit they will be asked for permission to assess their survival status via medical records.

6 Statistical Plan

The study design will allow multiple comparisons; specifically baseline to intervention group and cross-unit comparisons. The specific aim of the study is to pilot test **RESTORE resilience**, an individualized chronotherapeutic bundle, in pediatric patients supported on mechanical ventilation for acute respiratory failure in the PICU. The study design is a two-phase prospective cohort study. Subjects will be consecutively enrolled into the Baseline Phase and then into the Intervention Phase in two separate PICUs. Each unit will enroll 10 baseline subjects followed by 20 intervention subjects (total: 20 baseline subjects and 40 intervention subjects). Outcome variables are designed to be as objective as possible since it is not possible to blind the assessor to treatment phase.

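### Section 5.2 allows a child to be discontinued from the study for lack of adherence to R2, an outcome of the pilot, and nothing requires data collection to continue or names an analysis set

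*Combined protocol and SAP*

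**What the plan says.** Section 5.2 covers voluntary withdrawal and then removal by the investigator: "They may also be discontinued from the study at the discretion of the Investigator for lack of adherence to intervention". It gives no threshold and does not say whether non-delivery by staff counts. It also allows withdrawal for breach of the study plan, for safety and for administrative reasons.

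On what follows a removal, section 5.2 says "It will be documented whether or not each subject completes the study" and "Subjects who withdraw early will have one final visit to collect final evaluations and assess adverse events". Section 5.2.1, despite its general title, covers only consent withdrawal: "Subjects who withdraw consent to participate in the study will be seen for one final study visit", and "During this visit they will be asked for permission to assess their survival status via medical records".

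Section 2.2 lists among the secondary objectives "R2 feasibility, adherence, system barriers", and section 6.1 gives feasibility of delivering the whole bundle as the pilot's only interest. Section 3.3 has the local investigator or a designee complete an adherence form daily for each Intervention Phase child. Section 5 says of the other phase: "The study will not provide care recommendations or changes to treatment during the baseline phase". Section 6 explains that outcomes are kept as objective as possible "since it is not possible to blind the assessor to treatment phase".

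The primary outcome (section 6.3.2) is the average post-extubation ratio of daytime to 24-hour activity by actigraphy. The Study Summary compares it between Baseline Phase and Intervention Phase patients.

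**The concern.** The plan allows a child to leave the study because of a poor value on something the study sets out to measure. The decision is discretionary and unblinded, and the investigator who may remove a child may also be the person who scores adherence.

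The ground is one-sided. With no intervention at baseline, a Baseline Phase child cannot fail to adhere to it. The neighbouring ground, adherence to study procedures, applies in both phases and is not the issue here.

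The adherence result and the before-after comparison are both at stake. Section 6.2 intends the pilot's estimates for the power calculations of a future trial, so selection here would carry forward. Section 6.3 controls bias at entry, through consecutive approach, and through objective endpoints. It does not address selective exit.

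**Working it through.** **Plan figure.** Two sites × 10 baseline = 20; two sites × 20 intervention = 40; 20 + 40 = 60. This reproduces the total in section 6. The documents give no adherence rate, no removal rate and no definition of an adherent child, so no expected bias can be derived.

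**What a removal does to the data, from the text**

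1. Daily adherence forms (section 3.3): those completed before removal exist. Nothing requires later ones.
2. Activity ratio (section 6.3.2): actigraphy runs continuously from enrolment. A child removed after a recorded post-extubation day has a ratio, from fewer days. A child removed before that point has none, and one final visit cannot supply a 24-hour ratio.
3. Analysis: neither the Study Summary nor sections 6 to 6.3.2 name an analysis set or say how removed children are counted.
4. Direction: lost forms raise measured adherence if the poor adherence would have continued. Lost ratios favour R2 if non-adherent children would have had lower ratios. Both conditions are plausible, but the documents establish neither.

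**Illustration for adherence per child (assumed inputs).** Let A of 40 Intervention Phase children be adherent, and let k non-adherent children be removed and not counted. Observed adherence = A/(40 − k), so the true proportion A/40 is multiplied by 40/(40 − k), whatever A is.

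- Multiplier: k = 1, 40/39 = 1.03; k = 3, 40/37 = 1.08; k = 6, 40/34 = 1.18.
- A = 28 (28/40 = 70%): k = 1, 28/39 = 71.8%; k = 3, 28/37 = 75.7%; k = 6, 28/34 = 82.4%.
- A = 36 (36/40 = 90%): k = 1, 36/39 = 92.3%; k = 2, 36/38 = 94.7%.
- Removed but still counted: A/40, with no inflation.

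If adherence is instead summarised over daily forms, the forms kept from before removal shrink the inflation, but the later days are still missing. I give no figure for the activity ratio, since that would need an assumed SD and assumed ratios in non-adherent children.

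**The case against.** The strongest reply is that the harm needs steps the documents do not direct. The rule is discretionary and may never be used. Removal must also either come before a post-extubation day or be followed by dropping the child from the denominator. The clause reads like general template text: it mentions visit schedules in a study of intubated inpatients. Staff deliver most of the bundle, so if non-delivery does not count as lack of adherence, the ground covers little.

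There are also safeguards. Completion status is documented and early withdrawals get a final visit (5.2). Data are examined for systematic missingness (Study Summary), adherence reports are available for quality review (8.2), and adverse events are followed up (7.2). Section 8.1 keeps data collected before an authorization is revoked. Reasons for non-delivery are themselves a subject of study, through the objective on facilitating and restraining factors and the listing of system barriers. Finally, this is an exploratory pilot without a power claim.

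Most of this stands as a limit on size. Removals would leave a record, and the natural reading of the primary comparison sets no adherence condition. But a record of removals does not restore forms and actigraphy never collected, and it does not fix a denominator. Template or not, the clause is in force and conflicts with this study's own outcome. The lack of a power claim does not help, because feasibility is the stated interest.

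A reader might infer that removed children are excluded from the analysis. The documents do not say so; they are silent. A reader might also infer that the future trial would be undersized by a calculable amount. The documents give no SD and no adherence or removal rate, so no such figure is supported.

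**Conclusion.** The point holds in conditional form. Section 5.2 makes poor adherence a ground for leaving a study that measures adherence, and that ground exists in one phase only. No passage requires collection to continue after an investigator's discontinuation, and no analysis set is named. If the rule is used, adherence and the phase comparison can be selected in favour of R2.

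The size is unknown. The percentages above rest wholly on assumed adherence and removal counts and on a per-child measure that the plan does not define. The bias is small if adherence is high or removals are few, and per-child adherence is not inflated if removed children stay in the denominator. The wording should be fixed because the gap is plain in the text and cheap to close. Confidence is moderate, since the practical effect depends on how often the rule is used.

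Sections 4.2 and 4.5 also differ: one counts children with fully usable data, the other stops at 60 enrolled. That is a separate minor matter and adds no weight here.

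**What to change.** 1. In section 5.2, delete lack of adherence to the intervention as a ground for discontinuation from the study. State that the general grounds of breaching the study plan and administrative reasons do not include non-adherence to, or non-delivery of, bundle elements; otherwise they permit the same removals.
2. State that stopping a bundle element does not by itself end data collection. Actigraphy and daily forms continue to PICU discharge or Day 28 unless consent is withdrawn, the device is removed for skin irritation (10.1), or the child is withdrawn for safety under 5.2. No view is taken on the safety removals in 5.2 or the aspiration removals in 10.1. Those sections should only be reconciled on whether record-based data are still collected afterwards.
3. Keep all enrolled Intervention Phase children in the adherence and adverse-event denominators. Compare the primary outcome by phase of enrolment in all children with post-extubation actigraphy, whatever their adherence. Report by phase how many have no ratio and why.

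The cost is protocol wording, plus a few more days of collection with existing devices and staff for any child who would have been removed. Adherence and effect figures may look less favourable.
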